Aim 3: We will use logistic regression models to assess the utility of presence/absence of CAMLs after accounting for clinical factors and nodule characteristics. The primary analysis will be at the patient level, since this approach is most consistent with the potential future application of a validated CAML test in the clinic. The dependent variable will be a binary indicator of patient disease status as described for Aim 2 (1=diseased, 0=disease free). Independent variables will include presence/absence of CAMLs as well as factors previously identified in the literature as important predictors of lung cancer status including age, gender, smoking status, lesion diameter, spiculation, family history of lung cancer, emphysema, clear borders, and exposure to asbestos or other common pulmonary carcinogens.^{xv xvi xvii} When more than one lesion is detected in the same patient, lesion-specific covariate values (e.g., nodule diameter, spiculation) for that patient will be based on the nodule with highest risk of lung cancer. Continuous covariates may be modelled using restricted cubic splines to account for non-linear effects. As recommended by Pepe et al, Seshan et al and Vickers et al, the significance of the association between CAML test results and cancer status controlling for previously established clinical and radiological characteristics will be assessed using a Wald statistic from the multivariable logistic regression model (two-sided, 5% type I error).^{xviii xix} Table 2 displays detectable differences between CAML+ and CAML- patients from these multivariable^{xx}models, under a number of conditions.^{xxi} These estimates assume data are available from 1,000 patients with suspicious nodules (35 CAML+ and 965 CAML-), and approximately 3.5% of patients will subsequently have biopsy-confirmed lung cancer.

Table 2. Detectable differences in proportion with lung cancer between CAML+ and CAML – patients.

Squared multiple correlation between CAML status and other independent variables in the model	Detectable difference in the proportion with lung cancer between CAML+ and CAML – patients	Power
0.0	0.111	80%
0.1	0.118	80%
0.2	0.127	80%
0.3	0.138	80%

Table 3. Two-sided 95% confidence intervals for varied AUCs

AUC	Lower Bound	Upper Bound
0.80	0.71	0.89
0.85	0.77	0.93
0.90	0.83	0.97

0.95	0.90	1.00
------	------	------

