Receiver Operating Characteristic (ROC) curves and area under the ROC curve (AUC), with associated 95% two-sided confidence intervals, will be created to summarize the predictive accuracy of the model. Given the anticipated sample size, the upper and lower bounds for 95% two-sided confidence intervals for a range of possible AUCs are presented in Table 3.^{xxii} In addition, the performance of the model will be evaluated using leave-one-out cross validation.

In secondary analyses, we will test second-order interactions between presence/absence of CAMLs and other covariates to explore whether test performance differs among subsets of the population defined by demographic, clinical and nodule characteristics.

In exploratory analyses we will conduct nodule-specific analyses using methods similar to those described above. In this case, the dependent variable will be a binary indicator of nodule disease status (1=cancer detected, 0=cancer not detected). To account for the fact that some subjects may have multiple nodules, the logistic models will be fit using generalized estimating equation methods (GEE) (and robust variance estimates will be used for inference.^{xxiii} The power estimates in Table 2 are based on the assumption that there will be only 1 nodule per patient. Given that some subjects will have multiple nodules, the actual power of these exploratory analyses will likely exceed the stated estimates.

We will also evaluate the value of adding CAMLs to previously defined algorithms for evaluation of pulmonary nodules and the ability of CAMLs to potentially replace other known variables.

Trial feasibility: The trial calls for a total of 1000 evaluable patients accrued over 2 years. To assess the feasibility of this accrual rate, we examined the number of potentially eligible patients seen in the FCCC pulmonary clinic for FY 2017 (7/1/2016 to 6/30/2017). We found that there were over 1200 patients referred for evaluation of pulmonary nodules. The exact size of these nodules has not been captured in the data base, but the majority are within the indeterminate range. At the VA Philadelphia, the pulmonary nodule clinic performs over 1500 bronchoscopies/year and sees over 200 patients/year with pulmonary nodules measuring .8-3.0 cm. Therefore, between the two institutions, we feel confident that we will be able to enroll 1000 patients with indeterminate nodules within 24 months of activation.

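### Aim 3 fits CAML and nine other predictors to about 35 cancers without shrinkage, so predicted risks will be too extreme and the CAML odds ratio is overstated by an amount that grows with the true effect

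*Combined protocol and SAP*

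**What the plan says.** All of this is in section 9.0 of the combined protocol and SAP, under Aim 3.

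- **Model.** A patient-level logistic regression for biopsy-confirmed cancer. "Independent variables will include presence/absence of CAMLs as well as factors previously identified in the literature as important predictors of lung cancer status"; nine such items follow, covering age, sex, smoking, nodule size and appearance, family history, emphysema and carcinogen exposure.
- **Flexibility.** "Continuous covariates may be modelled using restricted cubic splines to account for non-linear effects". The number of knots is not given. Secondary analyses add interactions of CAML with the other covariates.
- **Test.** A Wald statistic for CAML ("two-sided, 5% type I error"). No penalty, shrinkage or limit on the number of terms is mentioned.
- **Size.** "These estimates assume data are available from 1,000 patients with suspicious nodules", split as "35 CAML+ and 965 CAML"-negative, and "approximately 3.5% of patients will subsequently have biopsy-confirmed lung cancer".
- **Model performance.** ROC curve and AUC, and leave-one-out cross-validation.
- **Existing algorithms.** "We will also evaluate the value of adding CAMLs to previously defined algorithms for evaluation of pulmonary nodules".

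**The concern.** With few events per parameter, ordinary maximum likelihood tends to push logistic coefficients away from zero. Two products of Aim 3 are exposed. The predicted risks spread too far towards 0 and 1, and section 2.2 wants a model of clinical factors with CAML to refine how nodule patients are assessed. The adjusted CAML odds ratio tends to be too large when the true effect is large, which favours the test under study.

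The concern is with those two outputs. It does not touch Table 2's detectable differences or the AUC precision in Table 3.

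**Working it through.** **1. The plan's own figures reproduce.** Table 2 ("Detectable differences in proportion with lung cancer between CAML+ and CAML"-negative patients) follows from the logistic sample-size formula for a binary covariate. With B = 0.035 CAML-positive and overall event rate P = 0.035:

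N(1 − R²) = {1.960·√[P(1−P)/B] + 0.842·√[P1(1−P1) + P2(1−P2)(1−B)/B]}² / [(P2−P1)²(1−B)]

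At R² = 0 and a difference of 0.111, P1 = 0.035 − 0.035 × 0.111 = 0.0311 and P2 = 0.1421. So N = (1.925 + 1.550)² / (0.01232 × 0.965) = 1,016. Solving for N = 1,000 gives 0.112, 0.119, 0.128 and 0.138, against the stated 0.111, 0.118, 0.127 and 0.138. The corresponding crude odds ratios are about 5.2 to 6.5. Tables 1 and 3 also reproduce.

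**2. Events per parameter.** Events: 0.035 × 1,000 = 35.

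| Reading of the covariate list | Slopes | Cancers per slope |
|---|---|---|
| CAML + 9 items, 1 df each | 10 | 3.5 |
| + three-level smoking (as on the On Study Form) and asbestos separate from other carcinogens | 12 | 2.9 |
| + 3-knot splines for age and diameter | 14 | 2.5 |
| + 4-knot splines instead | 16 | 2.2 |
| + 5-knot splines instead | 18 | 1.9 |

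**3. Effect sizes to test.** With 35 CAML-positive patients and 35 cancers, a PPV of p puts 35p cancers among CAML-positives and 35(1−p) among 965 CAML-negatives. At p = 0.50 that is 17.5/35 against 17.5/965 = 0.0181, a crude odds ratio of 1/(0.0181/0.9819) = 54. Conditional on covariates it is larger.

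**4. Simulation.** n = 1,000, about 35 CAML-positive and 35 cancers, fitted by ordinary maximum likelihood (ML) and by Firth's penalised likelihood. Covariate prevalences and effects are assumptions, because the documents give none. The ranges pool runs of 350 to 1,200 replicates with 10 to 16 slopes and differing assumptions. Ratios are medians or geometric means of estimated over true odds ratio.

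| CAML+ cancer proportion | Crude OR | Conditional OR | ML OR ÷ true OR | 95% Wald CI coverage |
|---|---|---|---|---|
| 0.143 (Table 2, R² = 0) | 5.2 | about 5.3-6.5 | 0.98-1.15 | 93.5-97% |
| 0.30 | 16 | 24 | 1.15-1.20 | 92-95% |
| 0.50 (Table 1, lowest row) | 54 | 100-106 | 1.28-1.69 | 90-94% (12-16 slopes); 94-95% (10 slopes) |
| 0.70 (Table 1, middle row) | 212 | 520 | 2.3 (12 slopes), 3.1 (16 slopes) | 92%, 87% |

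The upper end of the first row comes from a run at conditional odds ratio 6.5 in which CAML status depended strongly on the covariates; the CAML-positive cancer proportion there was about 0.26.

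- **Calibration slope on new data (ML, 12 to 14 slopes):** 0.61 to 0.87 across all scenarios.
- **Firth fit:** odds ratio 0.97 to 1.06 times the truth and coverage 93-97% up to a PPV of 0.50. The calibration slope moves only from 0.79 to 0.83 in the base case.
- **A prior risk score as one covariate plus CAML:** odds ratio within 1%, coverage 94-96%, calibration slope 0.94-0.99, provided the score is correct up to scale.

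**5. No CAML effect.** The Wald rejection rate was 3.5%. If CAML is unrelated to cancer, the chance that none of 35 CAML-positive patients has cancer is 0.965³⁵ = 0.29; the simulation gave 31%. In those trials the ML odds ratio does not exist, and the plan names no fallback. When CAML status depended strongly on the covariates this fell to 3%, and at a conditional odds ratio of 5.3 it was about 1-2%.

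**The case against.** The case on the other side is substantial.

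- **At the design effect the bias is small.** Near Table 2's effect a 7% overstatement is about 0.1 standard errors, inside an interval that spans a factor of about 3 each way. This stands. A reader might infer that the confidence interval is too narrow in general, or that a 40% overstatement is built into the plan. Neither follows: both appear only at the large effects that Table 1's PPV rows imply, and those rows are a precision grid, not a forecast. Nor is 40% a ceiling, as the PPV 0.70 row shows.
- **The plan never mentions an odds ratio.** It names a Wald test, an AUC and cross-validation, and the test is not inflated under no effect. A reader who concludes that the test or Table 2's power is invalid goes too far. The role of the odds ratio is inferred, although it comes from the same fit as the Wald statistic and would normally be reported with it. The predicted risks are tied to a stated objective.
- **The plan does not state 12 to 14 parameters.** Correct: the list gives 10 at minimum and splines are optional. With 10 slopes the overstatement was 4%, 16% and 28% at PPVs of 0.143, 0.30 and 0.50. That is smaller, with the same pattern.
- **There may be more cancers.** The 3.5% is close to the 100 − 96.4 = 3.6% true-positive share cited in section 1.1 for a screening trial that counted nodules from 4 mm; this study enrols 0.8-3.0 cm. At an assumed 7% the overstatement was 2-12% and coverage 93-96%. This is plausible, but the plan is sized on 3.5%.
- **Pilot data suggest a moderate effect.** Section 1.1 reports 63% positive in stage I and 18% in benign disease: (0.63/0.37)/(0.18/0.82) = 7.8, where bias is small. The same rates imply 0.63 × 35 + 0.18 × 965 = 196 CAML-positive patients, not the planned 35, so they do not settle the matter.
- **Leave-one-out cross-validation is planned.** It can expose the overfitting. It does not change the reported odds ratio, its interval or the predicted risks.

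**Conclusion.** The concern holds in a graded form. The firmest part is the predicted risks: with 35 cancers and no shrinkage they are too extreme in every scenario tried (calibration slope about 0.6 to 0.87). The odds-ratio part depends on the true effect: about 0-15% too high at Table 2's effect with near-nominal coverage, about 15-20% at a PPV of 0.30, and about 30-70% at 0.50 with coverage of about 90-94%. Separately, under no effect and with CAML independent of the covariates, about 30% of trials would have no finite ML odds ratio.

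These sizes rest on assumed covariate effects and prevalences, on the plan's 35 CAML-positive patients and 35 cancers, and mostly on CAML being independent of the covariates. Confidence is medium on the exact figures and higher on the direction. The change should be made before analysis because it is cheap.

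**What to change.** Amend Aim 3 in section 9.0 to state that:

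1. The multivariable model, including any interaction model, will be fitted by Firth penalised likelihood, and the CAML odds ratio reported with a profile penalised-likelihood 95% CI. This also gives a finite estimate if no CAML-positive patient has cancer. In the 1,200-replicate runs Firth coverage was computed with ±1.96 SE intervals; the profile interval was not simulated separately.
2. Predicted risks will be shrunk, by a uniform factor from the cross-validation already planned or by a ridge fit, with the intercept recalibrated and the calibration slope reported. Firth alone is not enough here.
3. In the comparison with existing algorithms, the prior algorithm's score enters as one covariate alongside CAML.
4. The coding of smoking and exposure and any spline knots are fixed in advance. Whether splines belong in the primary model is a preference: removing them changed the bias little (7%, 18% and 40% without, against 7-8%, 20% and 40-46% with 3-knot splines).

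Cost: SAP wording, a standard software option and a little more analysis. The reported odds ratio will be slightly smaller, and Firth predictions need an intercept correction. Recruitment, data collection and sample size are unaffected.

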3.0 Study Design

3.1 Description of Study Design, Population and Duration of Study Therapy

This is a multi-site diagnostic study. Individuals who are diagnosed with indeterminate pulmonary nodules will be eligible. They will undergo standard evaluation and follow-up as determined by their pulmonary physician. In addition, they will have at least one blood draw to evaluate for the presence (and quantity) or absence of CAMLs.

Subjects will be drawn from pulmonary nodule clinics at the Fox Chase Cancer Center and the VAMC Philadelphia. Approximately 1200 pulmonary nodule patients are evaluated annually at Fox Chase. Approximately 200 pulmonary nodule patients/year with

indeterminate nodules (i.e. 0.8-3.0 cm) are seen each year at the VA Philadelphia. Patients who are seen in these clinics will be asked to complete a questionnaire that will include demographic information (age, sex, zip code, smoking history, occupational exposures, military history (where relevant). Medical history will be obtained from the medical records. This information will include diagnoses (e.g. COPD, CAD etc.), medications (steroids, inhalers etc), smoking and other pulmonary carcinogen history and other information. Radiologic information including location of nodule (lobe), size, characteristics (ground glass, solid, spiculation etc) will be recorded (Appendices A, B).

Patient's blood would be drawn at 2 time points- at the time of detection of indeterminate lung nodules, and at the time of biopsy or beginning of therapeutic procedure. Each blood sample will be 10 cc of blood into two tubes equaling 20 cc per blood draw. Two tubes of blood will be drawn for each sample: one CellSave tube will be sent to Creatv for further analysis and one CellSave will be processed at the FCCC protocol support lab (PSL). Detection of CAMLs will be performed using the CellSieve™ microfiltration system according to established criteria. The CellSieve™ microfilter (Fig. 6) has low fluorescent background, enabling detailed visualization and characterization of the cells on the filter, which led to the discovery of the CAMLs. Figure 6 shows a scanning electron micrograph (SEM) of a CellSieve™ microfilter. The characteristics of these microfilters and the benefits are summarized here.

Properties	Benefits

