Number of years since last use:

(# of years) _____

Exposures:Asbestos exposure: No YesOccupational (specify)
_____Hobby (specify)
_____Residential (specify)
_____Random exposure: No YesIf yes, specify:
_____Agent Orange: No YesOther Occupational Exposure: No Yes

Confidential

Page 3 of 7

Medical History:

Family History:

- Lung cancer
- Head and Neck Cancer
- Bladder Cancer
- Esophageal Cancer
- Other (specify) _____

Other cancer, please specify: _____

Personal Medical History:

- COPD
- Reactive airways disease
- CAD
- Other pulmonary disease
- History of pneumonia

Height (cm): _____

((cm))

Weight (Kg): _____

((Kg))

Calculated BMI: _____

Pulmonary Function Tests

FEV1 (liters) _____

((liters))

FEV1 (% pred) _____

((% pred))

FEV1/FVC _____

DLCO _____

((numeric field))

DLCO % Predicted _____

((% pred))

Confidential

Page 4 of 7

Scan:

Date of Scan: _____

Characteristics of Nodule(s):

Nodule 1

- RUL
- RML
- RLL
- LUL
- LLL
- Lingula

Location:

Solid Semisolid

Size (cm):

((cm)) _____

Contour

- Smooth
- Spiculated
- Ground glass

If nodule is part solid/ground glass: % solid.

(% solid) _____

Calcification

- Not present
- Diffuse
- Central
- Laminated
- Popcorn
- Present, Not otherwise specified

Fat

Not present Present

Satellite nodules

Not present Present

Do you need to add another Nodule?

Yes No

Nodule 2

- RUL
- RML
- RLL
- LUL
- LLL
- Lingula

Location:

Solid Semisolid

Size (cm):

((cm)) _____

Contour

- Smooth
- Spiculated
- Ground glass

Confidential

Page 5 of 7

If nodule is part solid/ground glass: % solid.

(% solid)

Calcification

- Not present
- Diffuse
- Central
- Laminated
- Popcorn
- Present, Not otherwise specified

Fat

- Not present
- Present

Satellite nodules

- Not present
- Present

Do you need to add another Nodule?

- Yes
- No

Nodule 3

 RUL RML RLL LUL LLL Lingula

Location:

 Solid Semisolid

Size (cm):

((cm))

Contour

 Smooth Spiculated Ground glass

If nodule is part solid/ground glass: % solid.

(% solid)

Calcification

- Not present
- Diffuse
- Central
- Laminated
- Popcorn
- Present, Not otherwise specified

Fat

- Not present
- Present

Satellite nodules

- Not present
- Present

Do you need to add another Nodule?

- Yes
- No

Nodule 4

 RUL RML RLL LUL LLL Lingula

Confidential

Page 6 of 7

Density:	 Solid  Semisolid
Size (cm):	----- (cm))

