Contour	 Smooth  Spiculated  Ground glass
If nodule is part solid/ground glass: % solid.	
----- (% solid)	
Calcification	 Not present  Diffuse  Central  Laminated  Popcorn  Present, Not otherwise specified
Fat	 Not present  Present
Satellite nodules	 Not present  Present
Do you need to add another Nodule?	
 Yes  No	
Nodule 5	 RUL  RML  RLL  LUL  LLL  Lingula
Location:	
Density:	 Solid  Semisolid
Size (cm):	----- (cm))
Contour	 Smooth  Spiculated  Ground glass
If nodule is part solid/ground glass: % solid.	
----- (% solid)	
Calcification	 Not present  Diffuse  Central  Laminated  Popcorn  Present, Not otherwise specified
Fat	 Not present  Present
Satellite nodules	 Not present  Present

Confidential

Page 7 of 7

CAML (Cancer-Associated Macrophage-Like Cells) testing results:

CAML Date: _____

CAML cells present?

 Present Absent

CAML size

(microns) _____

CAML number

(numeric field) _____

CAML Comments

(free text field) _____

CTCs present?

 Present Absent

CTC number

(numeric field) _____

Apoptotic CTC

(numeric field) _____

EMT CTC

(numeric field) _____

CEVC present?

 Present Absent

CEVC number

(numeric field) _____

FOLLOW UP FORM

Confidential

Follow Up Form

Record ID

Date

Institution

 FCCC VA

Cigarettes:

 Never Active Quit since last time

Peak use (packs per day):

 < 0.25 0.25 0.50 0.75 1.00 1.25 1.50 1.75 2.00
 >2.00

Age at last use:

Number of years since last use:

(# of years)

Medical History:Family History: Change since last visit? Yes No

Family History:

- Lung cancer
- Head and Neck cancer
- Bladder cancer
- Esophageal cancer
- Other

Other cancer, please specify:

Personal Medical History: Change since last visit? Yes No

Personal Medical History:

- COPD

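### Aim 3 names emphysema and clear borders as covariates, but neither form has a field for them, and the contour item can undercode spiculation

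*Combined protocol and SAP*

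**What the plan says.** Section 9.0, Aim 3, sets out the covariates as a commitment: "Independent variables will include presence/absence of CAMLs as well as factors previously identified in the literature as important predictors of lung cancer status". After age and gender the list runs: "smoking status, lesion diameter, spiculation, family history of lung cancer, emphysema, clear borders, and exposure to asbestos or other common pulmonary carcinogens". The CAML effect is then tested by a two-sided 5% Wald test, adjusted for these factors.

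Section 3.1 says where the data come from. On medical records: "This information will include diagnoses (e.g. COPD, CAD etc.), medications (steroids, inhalers etc), smoking and other pulmonary carcinogen history and other information". On the scan: "characteristics (ground glass, solid, spiculation etc) will be recorded (Appendices A, B").

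The two appended forms are the only data-collection instruments shown. Personal medical history offers COPD, "Reactive airways disease", CAD, "Other pulmonary disease" and pneumonia. Each nodule block records location, density (solid or semisolid), size, contour, percent solid, calcification, fat and satellite nodules. The contour options read "Smooth Spiculated Ground glass", and a neighbouring item reads "If nodule is part solid/ground glass: % solid".

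**The concern.** Two of the factors that the model is said to contain have nowhere to be entered. A third, spiculation, shares an item with an attenuation category. If contour takes one answer, a nodule ticked Ground glass carries no margin information, and a nodule that is both spiculated and ground glass must lose one of the two descriptions.

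This matters because Aim 3 asks what CAML status adds once established predictors are accounted for. Section 9.0 also plans to add CAMLs to existing nodule algorithms and to ask whether CAMLs could replace known variables. Those comparisons are only as good as the recording of the known variables. A predictor that is absent or undercoded leaves part of its effect unadjusted. If it is related to both CAML status and cancer, the CAML coefficient picks up some of that effect.

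**Working it through.** **1. The covariate list against the forms.** The inputs are the Aim 3 list and the On Study Form. The Follow Up Form repeats the smoking, history and nodule items, adds the biopsy result, and fills neither gap.

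| Aim 3 factor | Field on the form |
|---|---|
| Age | yes |
| Gender | yes (sex) |
| Smoking status | yes (never, current, past) |
| Lesion diameter | yes (size in cm, per nodule) |
| Spiculation | yes, as one contour option |
| Family history of lung cancer | yes |
| Asbestos or other carcinogens | yes (asbestos, Agent Orange, other occupational) |
| Emphysema | none |
| Clear borders | none |

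Seven of nine factors have a field and two do not. COPD is the nearest history item and Smooth the nearest nodule item, but no text equates either with the named factor. The item for other pulmonary disease has no line to specify which disease.

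**2. Does the gap disturb the plan's own figures?** Table 2 gives detectable differences of 0.111, 0.118, 0.127 and 0.138 at 80% power for R² = 0.0, 0.1, 0.2 and 0.3. The formula for a binary covariate in logistic regression is

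N = [1.96·√(P(1−P)/B) + 0.842·√(p0(1−p0) + p1(1−p1)(1−B)/B)]² / [d²(1−B)(1−R²)],

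with B = 0.035 (35 of 1,000 CAML+), P = 0.035, p0 = P − B·d and p1 = p0 + d.

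For d = 0.111 and R² = 0:
- p0 = 0.0311 and p1 = 0.1421.
- The first term is 1.96 × 0.982 = 1.925.
- The second term is 0.842 × 1.842 = 1.550.
- N = 3.475² / (0.01232 × 0.965) = 1,016.

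The four rows need N = 1,016, 1,016, 1,008 and 999, against 1,000 planned. Solving for d at N = 1,000 gives 0.112, 0.119, 0.128 and 0.138. Table 2 therefore reproduces. The covariates enter it only through R², so neither the gap nor its repair changes any stated figure.

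**3. How much could the contour item blur spiculation?** The documents give no inputs, so these are assumptions: true odds ratio 2.5, spiculation in a share s = 10–30% of patients, and a fraction g = 5–50% of spiculated nodules ticked Ground glass and so counted as not spiculated. Overall risk is 3.5%, from Aim 3.

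Let q be the risk without spiculation and p1 the risk with it. The recorded non-spiculated group then has risk r0 = [(1−s)q + s·g·p1] / [(1−s) + s·g].

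- Mildest case (s = 0.10, g = 0.05): recorded odds ratio 2.48.
- Strongest case (s = 0.30, g = 0.50): q = 0.0246 and p1 = 0.0593, so r0 = (0.01721 + 0.00889)/0.85 = 0.0307. The recorded odds ratio is 0.0630/0.0317 = 1.99.

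The effect is attenuated, but the variable is not lost.

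**4. Can a model still be fitted?** In 300 simulated trials of 1,000 patients with assumed covariate effects and roughly 3% events, a logistic model gave stable estimates in 96%. It used the seven available factors, COPD in place of emphysema, no border term, and CAML status. Emphysema and borders had no effects of their own in the simulated data, so this speaks to fitting and not to bias.

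**The case against.** A reader might infer that the Aim 3 model cannot be fitted at all. The documents do not support that. Seven factors are recorded, a reduced model and its CAML Wald test can be run, and Section 3.1 draws on medical records with an open-ended list. Section 7.0 requires a chest CT at enrolment, so both missing items could be abstracted later. What stands is narrower: the listed model cannot be built from the form data, and no substitute is defined. Late abstraction also risks readings made with the biopsy result in view.

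A reader might also infer that spiculation is spoiled as a variable. It has its own option, and the percent-solid item lets a coder tick Spiculated and still describe attenuation. No instruction says to do so, however, and Section 8.0 allows either a radiologist or a pulmonary physician to measure. Undercoding is therefore foreseeable, but its extent is unknown.

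The single-choice reading is itself likely rather than certain. The text was extracted from PDF. Some nodule blocks show contour as radio buttons and others only as plain text. In the same extraction the biopsy histology options, which overlap, also appear as one radio group.

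Finally, a reader might infer that the gap makes CAMLs look better than they are. That is possible but not established. It needs the missing factors to be associated with both CAML status and cancer. Omitting a predictor of cancer unrelated to CAML status would instead pull the logistic coefficient towards the null.

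**Conclusion.** The mismatch is real and worth correcting. Two of the nine named factors have no field on either form and no defined proxy, which follows directly from comparing the list with the forms. Undercoding of spiculation is probable if contour takes one answer, which is held with less confidence. Under the assumed inputs, a true odds ratio of 2.5 would be recorded as 1.99 to 2.48.

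The consequence is an adjusted CAML effect controlled for fewer or less accurately recorded predictors than the plan states. The size and direction of any resulting bias cannot be derived from the documents.

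**What to change.** In the enrolment CT section of the On Study Form:

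- add emphysema (yes/no);
- add border (clear/not clear), per nodule;
- make spiculation its own yes/no item;
- record attenuation separately as solid, part-solid or ground glass.

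Complete these from the enrolment scan before the biopsy result is known. For patients already enrolled, back-fill from the enrolment scan with the reader blinded to biopsy and CAML results.

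If the sponsor prefers not to add fields, the minimum is to amend the Aim 3 list or define the proxies in Section 9.0 before the analysis.

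The cost is a few extra REDCap fields, read from a CT that is already required, and some back-filling. The sample size and Tables 1 to 3 need no change.

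### Table 2 prints 80% power in every row, but the formula behind it does not match the planned Wald test, which gives 77.5% in row 1 and less in the correlated-covariate scenarios examined for rows 2 to 4

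*Combined protocol and SAP*

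**What the plan says.** Section 9.0, Aim 3, names the test of CAML status: it "will be assessed using a Wald statistic from the multivariable logistic regression model (two-sided, 5% type I error"). The model also contains about nine patient and nodule factors, among them "age, gender, smoking status, lesion diameter, spiculation, family history of lung cancer, emphysema, clear borders".

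Table 2 is presented as the detectable differences for these models. Its inputs are 1,000 patients, of whom 35 are CAML+ and 965 CAML−, and the expectation that "approximately 3.5% of patients will subsequently have biopsy-confirmed lung cancer". Its rows are indexed by the "Squared multiple correlation between CAML status and other independent variables in the model":

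| R2 | Difference | Stated power |
|---|---|---|
| 0.0 | 0.111 | 80% |
| 0.1 | 0.118 | 80% |
| 0.2 | 0.127 | 80% |
| 0.3 | 0.138 | 80% |

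The reference attached to the table is a simple sample-size method for linear and logistic regression. Section 9.0 gives no covariate distributions or effects, and does not say whether the differences are marginal or covariate-adjusted.

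**The concern.** The table is calculated for one procedure and the analysis uses another. Two features of this design make that matter. In row 1 only about 5 cancers are expected among the CAML+ patients (35 × 0.142), so large-sample approximations are weak. In addition, logistic regression weights each patient by p(1−p), which is about four times larger in CAML+ than in CAML− patients. Multiplying the sample size by 1−R2 ignores that weighting.

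This is the only hypothesis test in the protocol with a stated power, and its purpose is to show that CAML adds to known predictors. The same section also leans on Table 2 when it says that the nodule-level analyses should have more power than the table states. An overstated power makes a non-significant result look more informative than it is.

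**Working it through.** **Inputs (section 9.0, Aim 3).** N = 1,000; CAML+ fraction B = 0.035; overall cancer rate P = 0.035; two-sided alpha 0.05. For a difference d, the CAML− risk is p0 = P − B·d and the CAML+ risk is p1 = p0 + d. Row 1: p0 = 0.0311, p1 = 0.1421. Row 4: p0 = 0.0302, p1 = 0.1682.

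**Step 1: reproduce Table 2.** A comparison of proportions with pooled null variance and N(1−R2) patients has

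power = Φ{ [√(N(1−R2)·d²·(1−B)) − 1.96·√(P(1−P)/B)] / √(p0(1−p0) + p1(1−p1)(1−B)/B) }.

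- Row 1: (3.448 − 1.925)/1.842 = 0.827, power 79.6%.
- Row 4: (3.587 − 1.925)/1.971 = 0.843, power 80.0%.
- Rows 2 and 3: 79.6% and 79.8%.

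Solving for exactly 80% gives differences of 0.112, 0.119, 0.128 and 0.138. The source of the table is therefore clear.

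**Step 2: the planned test in row 1.** At R2 = 0, take the unadjusted 2×2 Wald test of the log odds ratio. Sum the binomial probabilities over all outcomes of 35 and 965 patients for which |log OR| / √(sum of reciprocal cell counts) exceeds 1.96. Power is **77.5%**, and d = 0.116 gives about 80%. Simulated logistic fits with one or nine covariates, uncorrelated with CAML and without effect on cancer, gave 77–78%.

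Another large-sample formula would not repair this. Row 1 has log OR 1.641 and standard error 0.518, so Φ(1.641/0.518 − 1.96) is about 89%, well above the exact figure. The loss comes from the sparse CAML+ group.

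**Step 3: rows 2 to 4 with the N(1−R2) shrinkage only.** The same enumeration with 32 versus 868, 28 versus 772 and 24 versus 676 patients gives 77.2%, 78.2% and 78.0%. Rounding the half-patients the other way changes these by less than one point.

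**Step 4: rows 2 to 4 with actual covariate adjustment (scenarios).** Assume a normal covariate with equal variance in both groups, shifted by δ standard deviations between CAML+ and CAML−, and with no effect on cancer given CAML. Then δ² = [R2/(1−R2)] / [B(1−B)], and the large-sample variance inflation is 1 + f(1−f)δ², where f is the CAML+ share of the total p(1−p) weight.

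Row 4:
- δ² = 0.4286/0.03378 = 12.69.
- Weights: 35 × 0.1399 = 4.90 and 965 × 0.02926 = 28.24, so f = 0.148.
- Inflation = 1 + 0.148 × 0.852 × 12.69 = 2.60, against 1/(1−0.3) = 1.43 in the table.

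For rows 2 and 3 the inflation is 1.38 and 1.89, against 1.11 and 1.25. Simulated power of the multivariable Wald test, over normal, binary and (in row 4) skewed covariates, all without effect on cancer (roughly 1,500 to 4,000 trials per scenario, standard error about one point):

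| R2 | Difference | Simulated power |
|---|---|---|
| 0.1 | 0.118 | about 72–77% |
| 0.2 | 0.127 | about 66–74% |
| 0.3 | 0.138 | about 57–71% |

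In the normal-covariate case at R2 = 0.3 the test was also conservative, with type I error about 2%.

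**The case against.** The strongest reply is that Table 2 is a standard planning approximation, correctly computed from the method it cites, and that the shortfall on the protocol's own figures is only 2 to 3 points. That is right about the arithmetic: this is a mismatch of formula and test, not a miscalculation.

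The lower figures in Step 4 are open to three further objections, and all have force.

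- They depend on covariate shapes that section 9.0 does not give.
- They assume covariates without effect on cancer, whereas the model's covariates are chosen because they predict it. With uncorrelated prognostic covariates, simulated row 1 power was 79.7% in one case and 85.5% with a stronger effect. At R2 = 0.3, with 0.138 read as a marginal difference, it was about 6% or 92%, depending on the sign and size of the effect.
- R2 = 0.3 from one normal covariate needs a shift of √12.69 = 3.6 standard deviations. Nothing in the protocol says that so strong a separation is expected.

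A reader might therefore infer that the adjusted analysis really has 57–71% power, or that Aim 3 is underpowered. Neither follows. Row 4 may be no more than a sensitivity bound, and much larger effects are also contemplated. Table 1's lowest PPV of 0.5 implies p1 = 0.5, p0 = 17.5/965 = 0.018 and a difference of about 0.48, where power is close to 100% even at R2 = 0.3 with a normal covariate.

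The consequence is also limited: 1,000 is the expected accrual and is not shown to be derived from Table 2, and modelling is a secondary objective. The CAML+ count may itself change. The pilot rates in section 1.1 (63% in stage I, 18% in benign disease) would give 0.63 × 35 + 0.18 × 965, about 196 CAML+ patients rather than 35.

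What survives is that the printed 80% is not the power of the named test in row 1, and that a flat 80% in the other rows is unsupported.

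**Conclusion.** The concern holds as a mismatch between the power formula and the planned analysis. The firm part is row 1: 77.5% instead of 80%, or a difference of about 0.116 instead of 0.111. It rests only on the 35/965 split, the 3.5% overall cancer rate and a Wald test without prognostic covariates. If 3.5% is read as the CAML− rate, the figure is 76.0%.

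For rows 2 to 4, the document-based figure is about 77–78%. The larger shortfalls show that the 1−R2 adjustment can be materially too small for a sparse binary marker; they are not estimates of the power this study will have.

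**What to change.** State in section 9.0 whether the Table 2 differences are marginal or covariate-adjusted. Then restate the table from a simulation of the planned multivariable Wald test, with the assumed covariate distributions, their effects on cancer and their relation to CAML written out, and with whatever CAML+ count is finally adopted.

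Print either the power delivered at the listed differences (77.5% in row 1 on present inputs) or the larger differences needed for 80% (about 0.116 in row 1). The scenario ranges above should not be copied into the table; they only show why the simulation is needed. The later sentence comparing the power of the nodule-level analyses with Table 2 should be reread against the new figures.

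The cost is a short simulation and slightly less favourable stated figures. Neither the sample size nor the analysis has to change.
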